2.2.6.1 Genotypic resistance

Baseline and post-baseline genotypic resistance is defined as the presence of oseltamivir resistance mutations in the NA or HA genes identified by sequencing of influenza viruses isolated from nasopharyngeal samples.

Genotypic resistance calculation: Presence of genotypic resistance (yes/no), together with the specific resistance mutations will be identified (see USPI list in [Appendix 6](#)) for each nasopharyngeal sample and will be listed.

Note: a H274Y-specific RT-PCR assay was performed for some H1N1 samples of season 2008-2009 to determine baseline genotypic resistance and results will be also included.

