2.2.6.2 Phenotypic Resistance

Baseline and post-baseline phenotypic resistance is defined as the presence of phenotypic resistance identified by oseltamivir IC₅₀ determination, using statistical outlier rules and in accordance with the algorithm described in surveillance studies ([Sheu TG et al 2008](#), [Okomo-Adhiambo M et al, 2010](#)).

Phenotypic resistance calculation: The mean IC₅₀ of the baseline (pre dose Day 1 result) samples of all patients will be calculated separately for each virus subtype. Extreme outliers will be defined as any baseline or post-baseline IC₅₀ values > 10-fold the baseline mean IC₅₀. The baseline IC₅₀ distribution statistics (i.e. mean, standard deviation [SD], median, 75th percentile [X_{0.75}]) will then be re-calculated excluding any baseline extreme outliers previously identified. Outliers will be defined as any baseline or post-baseline IC₅₀ values less than 10-fold the baseline mean, but more than three interquartile ranges (IQRs) greater than the

baseline third quartile ($X_{0.75}$) ($> [X_{0.75} + \{3 \times IQR\}]$). Outliers and extreme outliers will be considered to have phenotypic resistance.

Note: the phenotypic resistance algorithm assumes that the IC_{50} samples are normally distributed. Appropriate transformations will be considered if this assumption is not met. Furthermore, alternative algorithms (e.g., fold-changes, pooling of NA subtypes) may be used if the number of IC_{50} samples per NA subtype is considered small.

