2.3 DETERMINATION OF SAMPLE SIZE

The sample size has been chosen to provide an adequate number of patients to estimate the development of resistance (genotypic and/or phenotypic) with reasonable precision. Assuming that 90% of enrolled patients will have laboratory-confirmed influenza, there will be 75 patients in each treatment arm in the population evaluable for the development of resistance. The following table shows the 95% Pearson-Clopper confidence intervals that would result with a sample size of 75 patients in a treatment arm if certain event rates are observed in the study.

Table 1 Expected confidence intervals associated to specific event rates

Observed Rate (%)	95% Confidence Interval
0.0	0.0-4.8
1.3	0.0-7.2
2.7	0.3-9.3
5.3	1.5-13.1
10.7	4.7-19.9

A total of 83 patients will be enrolled per arm and will be evaluable for the assessment of safety. This number of patients would provide estimates of adverse event rates with similar precision (see [Table 1](#)).

The sample size of 75 patients per group will have 66% power to detect a clinically relevant difference (CRD) between active treatment and historical placebo of 34 hours in time to resolution of symptoms, assuming a common standard deviation (SD) of 98 hours, using a 2-sided 10% alpha. The CRD and SD reflect those used to power the original study (original protocol). This has been calculated in EAST version 6.0, based on a Wilcoxon sign rank test. As no formal hypothesis will be tested in this study, the use of a 2-sided 10% alpha will be reflected by the use of 90% CIs.

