4.1.3 Modified Intent To Treat infected (mITT_i) Population

All patients randomized to a particular treatment, regardless of whether they received that treatment or not, and received at least one dose of study drug and with central laboratory confirmation of influenza infection, excluding patients infected with oseltamivir-resistant influenza at baseline, will be included in the mITT_i population. This population will also be used to summarize all efficacy and resistance endpoints because it will render least biased effect estimates. This population was not defined in the protocol.

The definition of oseltamivir-resistant influenza at baseline is defined in Section 2.2.6. Decisions on patient exclusion from the ITT, ITT_i and mITT_i population sets will be made by the statistician and study scientist after database closure. Excluded patients will be documented along with the reason for exclusion.

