4.7 RESISTANCE

To support the co-primary objective of this study, the proportion and Clopper-Pearson 95% CIs of patients with post-baseline genotypic or phenotypic resistance among all patients will be summarized by treatment group. The mITTi population will be used whenever possible.

In addition, the following outputs will be included:

- Incidence of overall post-baseline resistance (i.e. developed after first visit) by age (≥ 18 years vs < 18 years old) and treatment group, split by flu type and subtype.
- Incidence of overall baseline resistance (i.e. observed at first visit) by age and treatment group, split by flu type and subtype in ITT population. N.B. Patients with baseline resistance are excluded from both ITTi and mITTi populations.
- Profiles (listings) of viral load in \log_{10} vp/mL for patients with phenotypic or genotypic resistance at baseline. Also listings of genotypic resistance and phenotypic outlier samples.
- Incidence of known OC resistance mutations in phenotypic outlier samples compared with phenotypically OC sensitive samples.
- Incidence (in %) of post-baseline resistance in patients with detectable viral shedding (in \log_{10} vp/mL) at EOT and during follow-up period, by treatment group, age (≥ 18 years vs < 18 years old) and flu type and subtype.
- Summary (median and CI) of the TTR by treatment group, split by post-baseline resistance status.
- Summary (median and CI) of the TTR by treatment group in patients with post-baseline resistance, split by flu type.
- Summary of viral load in \log_{10} vp/mL for patients with phenotypic or genotypic resistance at baseline.

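### The co-primary resistance rate is taken over all mITTi patients, with no rule for those whose post-baseline resistance status is unknown

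*SAP*

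**What the plan says.** Section 4.7 supports the co-primary resistance objective with a proportion and Clopper-Pearson 95% CI per arm, the proportion being of patients with post-baseline "genotypic or phenotypic resistance among all patients will be summarized by treatment group". On the population it adds: "The mITTi population will be used whenever possible". Section 4.1.3 also assigns mITTi to the resistance endpoints. Patients enter mITTi if they were randomized, "received at least one dose of study drug and with central laboratory confirmation of influenza infection, excluding patients infected with oseltamivir-resistant influenza at baseline". Nothing after baseline is required beyond the dose.

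Resistance itself needs a typed sample. Section 2.2.6.1 has genotypic resistance "identified by sequencing of influenza viruses isolated from nasopharyngeal samples". Section 2.2.6.2 has "phenotypic resistance identified by oseltamivir IC₅₀ determination, using statistical outlier rules".

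Section 2.3 sizes the trial on the precision of this rate. It starts from "Assuming that 90% of enrolled patients will have laboratory-confirmed influenza" and concludes that "there will be 75 patients in each treatment arm in the population evaluable for the development of resistance".

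The missing-data section (4.9) covers symptom scores and temperature and does not mention resistance. One further output in section 4.7 gives post-baseline resistance among patients with detectable shedding at end of treatment and during follow-up.

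**The concern.** Two kinds of patient can lack a post-baseline sequence or IC50. The first was swabbed and had no virus left, so there was nothing to type, and calling that patient not resistant is reasonable. The second was not swabbed after baseline, or stayed PCR-positive with samples that could not be typed, and that patient's status is unknown. Section 4.7 does not separate the two. With all patients in the denominator and only typed samples able to reach the numerator, the second kind becomes a non-case by default.

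This can miss resistant patients but cannot add any. It also gives the interval a larger sample than was actually assessed. Both effects make resistance look lower and better estimated than it is, on a co-primary endpoint whose precision fixed the sample size. If the number of unknowns differs between doses, the side-by-side reading of the arms is affected too.

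The shedding output does not close the gap. It leaves out resistance found at earlier visits in patients who later cleared virus. It also leaves out patients with no late swab, and detectable shedding does not guarantee a typable sample.

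**Working it through.** **Inputs.** From section 2.3: "A total of 83 patients will be enrolled per arm", 90% laboratory-confirmed, 75 evaluable per arm, two-sided 95% Clopper-Pearson limits. The number of patients of unknown status is not in the SAP, so the values of 5 and 15 per arm used here are assumptions.

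**Formula.** For x events in n patients, the lower limit is the 0.025 quantile of Beta(x, n − x + 1), or 0 if x = 0. The upper limit is the 0.975 quantile of Beta(x + 1, n − x).

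**Step 1: reproduce the plan.** 83 × 0.90 = 74.7, which rounds to 75. So the evaluable number equals the laboratory-confirmed number, with no allowance for missed swabs or failed typing. On n = 75, x = 0, 1, 2, 4 and 8 give 0.0-4.8, 0.0-7.2, 0.3-9.3, 1.5-13.1 and 4.7-19.9. All five rows of Table 1 agree.

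**Step 2: take unknowns out of the denominator, 4 events.** Documented PCR-negative patients stay in.

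| Unknown | Denominator | Rate | 95% CI | Width (points) |
|---|---|---|---|---|
| 0 | 75 | 5.3% | 1.5-13.1 | 11.6 |
| 5 | 70 | 5.7% | 1.6-14.0 | 12.4 |
| 15 | 60 | 6.7% | 1.8-16.2 | 14.4 |

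With zero events, the upper limit moves from 4.8% on 75 to 6.0% on 60.

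**Step 3: worst case.** Counting 5 unknowns as resistant gives (4 + 5)/75 = 12.0% (5.6-21.6). With 15 unknowns, (4 + 15)/75 = 25.3%.

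**Step 4: coverage.** If only a fraction f of true cases can be detected and the rest are scored as non-cases, the event count is binomial with probability f × p on 75. The expected rate is then f × p. Coverage of the true p by the nominal 95% interval is:

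| True p | f = 1 | f = 0.9 | f = 0.8 | f = 0.7 | f = 0.5 |
|---|---|---|---|---|---|
| 5.3% | 96.6% | 96.5% | 95.7% | 93.9% | 86.6% |
| 10.7% | 97.7% | 97.5% | 95.9% | 92.6% | 77.2% |

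At p = 10.7% the expected rate is 8.6% for f = 0.8 and 5.3% for f = 0.5. At these two rates the exact interval is conservative enough to hold its level until roughly a quarter of cases go undetected. The bias in the point estimate is there from the first missed case.

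**The case against.** The SAP never says that untyped patients are scored as not resistant; this follows from the denominator, and the qualification on mITTi leaves some room. A reader might infer that every patient without a typable sample is miscounted. The documents do not support that: a patient swabbed on schedule and PCR-negative has no virus to type, and dropping all such patients would push the rate upwards.

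A reader might also infer a large effect, with perhaps only half the patients assessable. Nothing in the SAP supports such losses. Appendix 2 schedules six post-baseline swab visits (Days 2 or 3, 6, 8, 11, 15 and 40), allows swabs at home, and keeps patients who stop treatment early in follow-up. Few may be without any post-baseline swab. The share of positive swabs that cannot be typed is simply not stated.

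Nor does section 2.3 promise a population based on typing that section 4.7 then drops. Its evaluable number rests on laboratory confirmation, which is close to mITTi.

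Finally, whether a sample can be typed is known only after randomization and may depend on viral load, which dose may affect. Making typability define the main denominator therefore brings its own selection. That argument stands, and it is why the all-mITTi rate need not be replaced. None of these points supplies a rule for patients of unknown status or a count of them by arm.

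**Conclusion.** The concern holds in a limited form. Followed as written, section 4.7 turns patients of unknown post-baseline status into non-cases. The error goes one way, towards a lower rate and a narrower interval, and no planned output corrects it. It does not touch patients with documented negative PCR.

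The effect on the estimate is small if few patients are unknown: with 4 events and 5 unknown, 5.3% against 5.7%. It is moderate with 15 unknown, at 6.7%. The uncertainty is larger than those shifts suggest, since the same 5 unknowns allow a rate of up to 12.0%. These sizes rest on 75 patients per arm, 4 observed events and the assumed numbers unknown; the SAP does not supply the last. The known-status rate also assumes that patients of unknown status resemble the rest, which is why the bound belongs beside it.

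**What to change.** In section 4.7, before treatment allocation is released, classify each mITTi patient as one of:

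- resistant;
- known not resistant: typed and sensitive, or PCR-negative after baseline;
- unknown: no post-baseline swab, or only PCR-positive swabs that could not be typed.

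PCR-negative should mean a recorded result. The rule in section 2.2.2.3 that treats later missing values as negative was written for shedding and should not be used to assign status here. The text should also say where a patient with an untyped positive swab followed by a negative one belongs, because the definitions above place that patient among the known not resistant.

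Report the number unknown by arm. Keep the all-mITTi rate. Beside it give the rate with Clopper-Pearson CI among patients of known status, and a bound that counts every unknown as resistant.

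The cost is some SAP wording, one extra table and a somewhat wider interval for the known-status rate. No new data are needed.

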4.8 VIROLOGY

The main virology outputs are:

- Incidence of persistent shedding (%), defined as $< 1 \log_{10}$ viral load (vp/mL) reduction at end of treatment compared with baseline.
- Summary of IC_{50} at baseline and fold-change over time by treatment group split by flu type and subtype using descriptive statistics: mean, SD, median, IQR, range.

- Summary of viral load in \log_{10} vp/mL for patients with resistant phenotype or genotype at baseline (ITT).
- Summary of viral load change from baseline over time in \log_{10} TCID₅₀ (viral culture) (adults mITTi).
- Summary of viral load change from baseline over time in \log_{10} TCID₅₀ (viral culture) (paediatrics mITTi).
- Summary of viral load change from baseline over time in \log_{10} vp/mL (RT-PCR) (adults mITTi).
- Summary of viral load change from baseline over time in \log_{10} vp/mL (RT-PCR) (paediatrics mITTi).
- Incidence of patients with viral shedding in \log_{10} TCID₅₀/mL and in \log_{10} vp/mL by visit (adults and adolescents mITTi)
- Incidence of patients with viral shedding in \log_{10} TCID₅₀/mL and in \log_{10} vp/mL by visit (paediatrics mITTi).

4.9 MISSING DATA

As no formal statistical analyses will be carried out, imputation methods for missing data for the purposes of statistical model fitting are not required.

For the derivation of time to resolution of symptoms endpoints, a missing symptom score will be estimated by linear interpolation between the previously available assessment and the subsequent available assessment. (More details are provided in [Appendix 7](#)).

For the derivation of time to resolution of fever, a missing temperature entry will be estimated by linear interpolation between the previously available assessment and the subsequent available assessment.

4.10 INTERIM ANALYSES

No efficacy interim analyses are planned.

6. APPENDIX 1: PROTOCOL SYNOPSIS

TITLE: A DOUBLE BLIND, RANDOMIZED, STRATIFIED, MULTI-CENTER TRIAL EVALUATING CONVENTIONAL AND DOUBLE DOSE OSELTAMIVIR IN THE TREATMENT OF IMMUNOCOMPROMISED PATIENTS WITH INFLUENZA

PROTOCOL NUMBER: NV20234

VERSION NUMBER: F

EUDRACT NUMBER: 2006-002468-24

IND NUMBER: 53,093

TEST PRODUCT: oseltamivir (Tamiflu® RO 64-0796)

PHASE: IIIb

INDICATION: Treatment of influenza in immunocompromised patients

SPONSOR: F. Hoffmann-La Roche Ltd

Objectives

Primary

To evaluate prospectively the safety and tolerability of oseltamivir for the treatment of influenza in IC patients under standard and double dose, and characterize the effects of oseltamivir in IC patients on the development of resistant influenza virus (see 4.6).

Secondary

To evaluate the effects of conventional and double dose oseltamivir in IC patients on:

- The population pharmacokinetics of *both oseltamivir and oseltamivir carboxylate* in IC patients with confirmed influenza infection, through the application of established population pharmacokinetic (PK) models to the sparse plasma concentration data generated.
- The virologic course of influenza (proportion shedding and viral loads at different timepoints)
- The time to resolution of influenza symptoms
- The clinical course of influenza (fever, symptoms, secondary illnesses as evidenced by otitis media, bronchitis, pneumonia, or sinusitis)
- To explore the relationship of metrics of exposure (e.g., AUC, C_{min}) to relevant pharmacodynamic endpoints

Study Design

Description of Study

This is a double-blind, randomized, multi-center trial of twice daily, conventional and double dose oseltamivir for the treatment of influenza in IC patients. Patients will be stratified by age (<13 vs. >12 years), transplant status (yes vs. no), time since onset of flu symptoms and treatment start (up to 96 hours) (≤ 48 vs. >48 hours) and vaccination status (yes vs. no).

Number of Patients

A minimum of 166 (83 per arm) to allow an adequate number of influenza A patients per arm; including 50 transplant recipients *and at least 15 paediatric patients*.

Number of Centers

Approximately 125 centers in the Northern and Southern Hemispheres

Target Population

Patients immunocompromised due to a primary or secondary immunodeficiency, 1 year of age and older (*the paediatric and adolescent patients will be defined as 1 year to less than 18 years of age*). The patients will be positive for influenza by a rapid diagnostic test, PCR or viral culture at baseline.

Length of Study

The study comprises 10 days of treatment with follow up visits approximately 5 and 30 days later as shown in the schedule of assessments. Study medication will be administered twice daily over 10 days for a total of 20 doses. A rapid diagnostic test for influenza will be performed at the end of the 10 days of treatment. Patients still having influenza based on the rapid diagnostic test will be treated per the local standard of care by the principal investigator, and any medication provided during the follow-up period should be captured in the CRF.

Procedures (summary)

The key procedures are:

- Blood draws for serum chemistry, hematology, serology, and PK assessments (for those patients who provide additional consent to participate in the PK assessments).
- Nasal and throat swabs for viral culture and RT-PCR.

Assessments of:

Safety

The safety laboratory assessments in this study, including the assessment of serum chemistry and hematology will be carried out at a central laboratory. Serum chemistry assessments comprise AST, ALT, total bilirubin, urea and creatinine. Hematology assessments include CBC and differential count. The total volume of blood loss for laboratory assessments will be approximately 20 mL for the entire duration of the study.

Protection of patient confidentiality (Section 16) will extend to any data generated from the assaying of these samples. Biological samples taken from all patients may be infectious and will be classified as “diagnostic specimens” for dispatch purposes.

When clinically indicated, the investigator may draw blood for serum creatinine to be assessed at the local laboratory during the study to calculate creatinine clearance

Resistance

Development of resistance

Efficacy

The efficacy laboratory assessments are used for laboratory confirmation of influenza. These are:

Nasal and throat swabs. Two nasal and one throat swab will be collected as described in the Schedule of Assessments. All swabs are sent to a central laboratory for RT-PCR and viral cultures. Influenza virus shedding will be assessed.

At the end of treatment (Day 11), a rapid diagnostic test is permitted for the diagnosis of ongoing influenza.

Investigational Medicinal Products

Test Product:

Oseltamivir/placebo dry powder (to be reconstituted to a concentration of 12 mg/mL *or 6 mg/mL [the 6 mg/mL will only be used if applicable and not before 2015]*) and 75 mg capsules. The duration of dosing in both adults and children is 10 days.

Conventional dose:

Children ages 1–12 years: Oseltamivir syrup

≤ 15 kg 30 mg twice daily

15–23 kg 45 mg twice daily

23–40 kg 60 mg twice daily

>40 kg 75 mg twice daily

Adults and adolescents (age ≥ 13 years): Oseltamivir capsules 75 mg twice daily

Patients randomized to the conventional dose will simultaneously receive matching placebo so as to blind them and the investigator from the double dose arm.

Double dose:

Children ages 1 - 12 years: Oseltamivir syrup

≤ 15 kg 60 mg twice daily

15–23 kg 90 mg twice daily

23–40 kg 120 mg twice daily

>40 kg 150 mg twice daily

Adults and adolescents (age ≥ 13 years): Oseltamivir capsules

150 mg twice daily

Comparator:

Placebo (from pivotal registration trials in otherwise healthy adults)

Statistical Methods

The sample size has been chosen to provide an adequate number of patients to estimate the development of resistance with reasonable precision. Assuming that 90% of enrolled patients will have laboratory-confirmed influenza, there will be 75 patients in each treatment arm in the population evaluable for the development of resistance. The following table shows the 95% Pearson-Clopper confidence intervals that would result with a sample size of 75 patients in a treatment arm if certain event rates are observed in the study.

During the study the number of influenza A virus infected patients and the rate of development of resistance will be monitored in a blinded fashion, in order to ensure a reasonable precision for the estimation is maintained. Additional patients may be enrolled if necessary.

Table A1.1. Confidence interval given the rate of events

Observed Rate (%)	95% Confidence Interval
0.0	0.0%–4.8%
1.3	0.0%–7.2%
2.7	0.3%–9.3%
5.3	1.5%–13.1%
10.7	4.7%–19.9%

A total of 83 patients will be enrolled per arm and will be evaluable for the assessment of safety. This number of patients would provide estimates of adverse event rates with similar precision.

For the primary objective of evaluating the safety of oseltamivir conventional and double dose treatments, AEs, physical examinations, tissue rejection and/or graft versus host disease in transplant patients, laboratory tests, and vital signs will be summarized and compared with the known safety profile of the drug. For the summary of the development of resistance for each treatment arm, 95% confidence intervals will be provided with the estimated rates.

For the secondary objective of evaluating the efficacy of oseltamivir as measured by the time to resolution of influenza symptoms, the following two assessments will be made independently of each other and without regard to the outcomes in each case.

- Comparison to placebo control from pivotal registration trials

From the integrated efficacy database associated with the oseltamivir treatment approval, a population of placebo treated patients will be established that is comparable to patients in the current study whose first dose of study drug was within 48 hours of symptom onset. For this population, a median time to resolution of all clinical influenza symptoms will be determined along with its 95% confidence interval.

- Assessment of relative efficacy

The two dose groups will be compared to each other by estimating the difference in the median times to alleviation of symptoms and deriving an associated 95% confidence interval.

The following are the model-derived PK secondary endpoints for *oseltamivir and oseltamivir carboxylate*: steady-state AUC, C_{max} , and C_{trough} .

7. **APPENDIX 2: SCHEDULE OF ASSESSMENTS**

Table A2.1. Schedule of Assessments and Procedures

	Baseline	Treatment					Follow-up		
Study Day	1 (pre-dose)	1	2 or 3 ^{f,g}	6 ^{f,g}	8 ^{f,g}	11 ^{g,h,i}	15 ^g	40 ^{g,j}	
Informed Consent/Assent ^l	x								
Medical history	x								
Demographics	x								
Height and weight	x					x			
Pregnancy Test ^a	x					x		x	
Rapid diagnostic test for influenza virus shedding						x			
RIDTPCR/Culture for confirmation of influenza virus	x								
Safety Labs ^b	x					x			
Physical Examination	x					x		x	
Vital Signs (including pulse, respiratory rate, temperature, blood pressure)	x		x	x	x	x	x	x	
Nasal and throat swabs for viral shedding and viral load ^{c,d}	x		x	x	x	x	x	x	
PK sampling (blood) ^l						x ^m			
Review of patient diary data ^e			x	x	x	x	x	x	
Drug Administration		←—————→							
Collection of unused study drug and empty containers						x			
Previous Diseases	x								
Previous/Concomitant medications	x	←—————→							
Adverse Events/Sec Illnesses and Treatments		←—————→							
Rejection, Graft versus host disease (GVHD)		←—————→							

- a. Urine pregnancy test for patients of child-bearing potential according to the judgment/discretion of the investigator.
- b. Hematology (CBC with differential) and chemistry (AST, ALT, total bilirubin, urea, Cr). Serum creatinine testing may be done at a local laboratory when clinically indicated to calculate creatinine clearance.
- c. Baseline swab samples will be assessed for the presence of resistance mutations.
- d. Two nasal and one throat swab for viral culture and RT-PCR.
- e. Influenza symptoms, temperature, and date/time of oseltamivir dose will be recorded by the patient in the patient diaries twice daily on Days 1 – 10, and once daily thereafter.
- f. A home visit may be made on Day 2 or 3 (for patients who are too ill to come into the clinic) and/or, Day 6, and/or Day 8; however, it is recommended that the PK blood draw be performed at the clinic.
- g. Day 2/3 visit window = + 1 day. Day 6 visit window = ± 1 day; Day 8 visit window = + 1 day. Day 11 visit window = ± 1 day. Day 15 and Day 40 visit occur approximately 5 and 30 days after the last dose respectively. Day 15 window = ± 1 day. Day 40 window ± 2 days.

- h. Only weight to be assessed. Height is not necessary at this visit. Study drug is taken on Day 11, only if the first dose was taken after 4 p.m. on Day 1.
- i. Patients who are rapid diagnostic positive can be treated per standard of care. They will be required to come for their follow-up visits on Day 15 and Day 40.
- j. Patients who discontinue treatment prematurely will have an end of treatment (Day 11) assessment at the time of treatment discontinuation or the following day. They will be required to attend their follow up visits approximately 5 and 30 days after the last dose (Day 15 and Day 40 assessments).
- k. Patients who discontinue during follow-up will have an end of follow-up (Day 40) assessment. This visit must occur within 30 days of the last dose.
- l. For patients who are unable to attend the clinic, swabs may be taken at home on those days where there is a home visit by site personnel.
- m. Plasma PK samples for assessment of oseltamivir and oseltamivir carboxylate will be collected from patients who give additional consent to participate in PK sampling using a sparse PK sampling approach.
- n. Serial PK samples taken at steady-state no earlier than Day 6 (i.e., not before the 11th dose) consisting of as many of the four timepoints as possible: within 30 minutes prior to the dose administration, 1.5 hours \pm 30 minutes post dose, 4 hours \pm 60 minutes post dose, and 8 hours \pm 1.5 hours post dose (for patients who have given additional consent).

